6.3.4 Concomitant Medications

At annual study visits concomitant medications of interest taken since the last visit will be recorded in the source documentation and entered into the concomitant medication log CRF.

6.3.5 *ARV Modifications*

All modifications of ART, including initiation of ART, will be recorded on the CRF's at the 3 month data extractions: including initial doses, patient-initiated interruptions, modifications, and permanent discontinuations. ART will also be reviewed and confirmed at the annual study visits.

6.3.6 Clinical Assessments

Height and Weight

Height and weight should be documented at study entry and weight documented at annual visits.

Treatment-Limiting Toxicity and Diagnoses

The following should be recorded on the CRFs at the annual study visits, and upon reaching the primary endpoint of LTFU (if possible): AIDS-defining events, ART-limiting toxicity, CV events or non-AIDS-related malignancies, STI diagnoses, new medical conditions and death. The source document must include date of diagnosis and date of resolution.

6.3.7 *Immunologic and Virologic Studies*

Nadir CD4+ T-Cell Count

The subject's prior nadir CD4+ cell count (absolute value and date) should be documented during screening and, when possible, a copy of nadir CD4+ cell count report should be included in the source document. If this documentation is not available, then subject recollection will suffice. For

Subjects who do not know the exact nadir value and for whom there is no source documentation, then recall of the categorical nadir (e.g., < 50, < 100, < 200 cells/mm³) will suffice.

CD4/CD8 and HIV-1 RNA

At baseline, at all annual study visits, and upon reaching the primary study endpoint (if possible), a CD4/CD8 count and percentage and HIV-1 RNA will be recorded. The results may be obtained via chart extraction, if available from a CLIA-certified laboratory within 60 days of the study visit. If a result is not available within a 60 day window, it will be drawn at the study visit.

To avoid the need for extra blood draws, efforts will be made, via communication with the Primary Care Provider, to have the patient's routine primary care blood draws occur within the 60 day window of the annual study visits.

6.3.8 Antiretroviral resistance testina

If patients have had an antiretroviral resistance test during routine care, that data will be collected via chart abstraction.

6.3.9 Stored Samples

Stored plasma will be collected at study entry, the annual study visits, and upon reaching the primary study endpoint (if possible). Specimen collection will be encouraged but not mandated. Specimens will be stored at the site's local laboratory and batched shipped to the central laboratory (UCSD) after completion of the study.

Blood volume for stored plasma: 15mL

6.4 End of Study Assessment

At end of study subjects will be asked (in person or by phone) to complete a short questionnaire assessing the subjects' experiences over the course of the study. Subjects in the intervention will be asked specifically about the different components of the intervention and about other aspects of care that may impact their retention in care. Subjects in the standard of care arm will be asked about aspects of care that may impact retention in care. The survey will be administered to patients

who verbally consent to participate. No personal health identifying

information will be collected as part of this survey.

7.0 CLINICAL MANAGEMENT ISSUES

7.1 Toxicity

No toxicities are anticipated as no treatment or invasive procedures are being performed as part of this study.

8.0 CRITERIA FOR EARLY TERMINATION

8.1 Criteria for Study Subject Discontinuation

8.1.1	Pregnancy or initiation of breastfeeding during the study.
8.1.2	Subject request to withdraw participation.
8.1.3	Primary care provider request for subject withdrawal based on the provider's belief that study participation is no longer in subject's best interest.
8.1.4	Medical provider belief that the patient has life threatening clinical condition.
8.1.5	By the discretion of the site IRB, CCTG, or investigator.
8.1.6	The patient is found to be incarcerated at the time of reaching the primary endpoint.

9.0 STATISTICAL CONSIDERATIONS

This section briefly describes the planned statistical analysis. The *Statistical Analysis Plan* (SAP) provides details. If the language in this section differs from the language in the SAP, the SAP takes precedence.

9.1 General Design Issues

This is a 48-week, un-blinded, 2-arm, randomized (1:1) controlled clinical trial.

9.2 Endpoints

Primary Outcome: The CCTG 594 primary outcome is "time to LTFU" defined as the time from baseline visit to meeting the primary endpoint (LTFU defined as: no visit with a prescribing provider for more than 180 days).

9.3 Randomization and Stratification

Once eligibility and consent are confirmed and the baseline survey is completed, randomization will occur using the web-based CFAR BIT data management system. Participants will be randomized (1:1) to either the ALERT Enhanced Retention Intervention Arm or the SOC Arm by the study coordinator or ALERT specialist.

We will stratify randomization by whether the patient is a new HIV diagnosis or a prior diagnosis returning to care and by HIV primary care clinic site.

9.4 Sample Size and Accrual

9.4.1 Power and Sample Size Justification

The primary outcome for this study is to compare the time to LTFU. A secondary outcome is time to initiation of ART. Sample size calculations were based on a two-sided, two-sample log-rank test to compare the differences in time to the-primary endpoint proportions between the intervention arm and the standard of care arm.

Since attrition is a component of the composite endpoint, attrition rates are not used as an adjustment in the power calculations. Assuming 150 subjects per group in each of the two

Table 5: Power based on a two-sided, log-rank test with alpha=0.05 and N=150 per arm (total N = 300)							
Composite	Composite rate	Corresponding	Statistical				
rate without	without	Hazard Ratio	Power (%)				
Endpoint in	Endpoint in	(HR)					
SOC (%)	Intervention						
	(%)						
65	80	1.93	82				
65	85	2.65	97				
70	85	2.19	87				
75	87.5	2.15	78				
75	90	2.73	92				
80	92.5	2.86	87				
80	95	4.35	97				

groups (for a total of 300 subjects), we have 87% power to detect a difference of 15%, assuming a time without a composite endpoint rate of 70% in SOC arm and that the intervention arm will increase the time without an endpoint (to a rate to 85%). This corresponds to a hazard ratio of 2:19. Table 5 shows other possible standard of care rates between arms (and hazard ratios), and corresponding statistical power. The calculations assume that the hazard rates are proportional.

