It is expected that subjects new or returning to care will have regular primary care visits at least 3-4 times in the first year. The ALERT specialist will use the clinic medical record system to abstract data on clinic visits, ART medications, serial HIV RNA and CD4 values, routine CBC and chemistry values, HIV-related and AIDS diagnoses and other medical diagnoses. Data will be entered into the study electronic database. Abstraction will be done at least quarterly for each subject. The ALERT specialist will track the status of each subject and record retention and outreach in the study database. Using data abstracted from the primary care clinic medical records system, the ALERT specialist will record all visits with a prescribing HIV provider, which will document retention as related to the primary study endpoint. For patients in the SOC arm, contact information will be collected for use in the event that the person meets the primary endpoint. Subjects in either arm who reach criteria for the LTFU primary endpoint will be identified by the ALERT specialist. The ALERT specialist will then contact the subject to assure that the patient is not incarcerated or receiving care from an HIV provider at

another facility. Once LTFU is confirmed, the ALERT worker will try to bring the patient in for a primary endpoint visit. All patients will continue to be followed after the primary endpoint (ITT) for assessment of secondary endpoints.

Education Contacts (weeks 1-24). The ALERT specialist will complete a 5 session educational curriculum called a retention module either in person or by phone to the subjects randomized to the ALERT Intervention arm. The 5 retention modules include instruction about the navigation of HIV health systems, HIV literacy, Disclosure, Medication adherence and Continuation with Care, and Self-Efficacy [MOP CCTG 594: 5.0 The 5 Retention Modules for the ALERT specialist]. The goal will be to present the majority of the material within the first 6 months, however scheduling flexibility will be allowed up to the 12 month time-point in order to maximize opportunities for patients to receive the intervention. Subjects that complete all 5 modules will be asked about their reasons motivating them to 1) participate in the study and 2) completing the 5 modules.

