9.6.2 Analysis of Primary Outcome

A survival analysis of "time to LTFU" will be conducted. LTFU is defined as no visit with a prescribing HIV provider in the last 180 days. Time-to-LTFU will be calculated as total days between the first visit and the date when the participant reaches the definition of LTFU.

For example, a subject has his first visit on Jan 1, 2013, and another visit on Mar 1, 2013. If the subject does not have any visits thereafter, or does not have any visits until >180 days later, the subject will be counted as reaching the primary endpoint of LTFU. In this case, the subject would be LTFU if no visit occurred before Aug 27, 2013, (which is 180 days past Mar 1st). The "time-to-LTFU" will be the time period between Jan 1, 2013 and Aug 27, 2013.

At the end of the study, patients who have not reached the primary endpoint will be censored at the time of their last quarterly data extraction.

Patients who meet the primary endpoint and are found to be incarcerated will be removed from the study and censored effective at the time of their incarceration. Those who are incarcerated but return to care upon release, prior to reaching a primary endpoint, will be allowed to remain in study. Patients who change care provider to an external health facility (such as a different clinic system or a nursing facility) will be assessed for their current engagement in care; those who have completed a clinic visit with a prescribing clinician within the 180 days will be considered engaged in

care, and will not be considered LTFU. If possible, these patients will continue to come in for annual study visits.

The null hypothesis is that the median time-to-LTFU estimated using the Kaplan-Meier method will be identical in both groups. The log-rank test will be used to test the null hypothesis against the alternate hypothesis that the median time-to-LTFU is not the same between the groups.

In addition, to assess the factors associated with time-to-LTFU, Cox regression models will be performed on two subgroups, looking at each arm separately. The model will have time to LTFU as the outcome, baseline variables such as demographic, socioeconomic, psychosocial factors, risk behavior, substance use and psychiatric illness as predictors.

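### Does leaving out an attrition allowance, on the ground that attrition belongs to a composite endpoint, leave the trial underpowered or biased?

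*Combined protocol and SAP*

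**What the plan says.** Section 9.4.1 gives 87% power for a two-sided 0.05 log-rank test with 150 patients per arm, "assuming a time without a composite endpoint rate of 70% in SOC arm" and 85% in the ALERT arm. It explains the missing dropout allowance this way: "Since attrition is a component of the composite endpoint, attrition rates are not used as an adjustment in the power calculations". Table 5 uses the same composite label for its rates.

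The Schema and sections 1.2.1, 3.0, 9.2 and 9.6.2 all name a single outcome, time to LTFU. Section 9.2 has "LTFU defined as: no visit with a prescribing provider for more than 180 days".

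Section 8.1 lists six reasons for stopping, among them "Subject request to withdraw participation". Only incarceration has its own analysis rule. Under 9.6.2, patients who meet the endpoint and are "found to be incarcerated will be removed from the study and censored effective at the time of their incarceration". Otherwise, at study end, "patients who have not reached the primary endpoint will be censored at the time of their last quarterly data extraction".

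Section 6.2.4 has visit data abstracted from charts at least quarterly for every subject, and adds: "All patients will continue to be followed after the primary endpoint (ITT) for assessment of secondary endpoints". Section 9.6.1 analyses everyone randomized. Section 9.0 leaves detail to a separate SAP: "If the language in this section differs from the language in the SAP, the SAP takes precedence".

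**The concern.** The reason given for ignoring attrition refers to an endpoint the trial does not have. Under a true composite of LTFU or study exit, every exit would be an event and no allowance would be needed. With LTFU alone, a patient who withdraws, becomes pregnant or is withdrawn by a provider has not had the event. If chart abstraction stops at that point, the patient is censored and the event count falls. Incarceration goes further, turning a met endpoint into a censored time.

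Two things would be at stake. One is power: 87% would hold only with no non-LTFU censoring. The other is bias: a patient who asks to leave while drifting out of care is close to the event. In an unblinded trial where one arm has far more study contact, such exits could differ by arm. For 8.1.1 to 8.1.5 the supplied text does not say whether abstraction continues.

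**Working it through.** **Inputs from section 9.4.1.** 150 per arm, two-sided alpha 0.05, event-free rates 70% (SOC) and 85% (ALERT), no attrition. The time point of these rates is not named; 48 weeks (336 days) is assumed below.

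**Reproducing the 87%.**
- HR = ln(0.70)/ln(0.85) = 2.195.
- Expected events d = 150 × 0.30 + 150 × 0.15 = 67.5.
- Freedman power = Φ(√d × (HR − 1)/(HR + 1) − 1.96) = Φ(8.216 × 0.374 − 1.96) = Φ(1.112) = 86.7%.

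The seven rows of Table 5 come out at 82.2, 97.5, 86.7, 78.4, 91.9, 87.2 and 97.0%, against 82, 97, 87, 78, 92, 87 and 97% printed. The arithmetic is sound.

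**Power with non-LTFU exits.** The documents give no exit rate, so p is an assumption, equal in both arms.
- Spread exits: constant LTFU hazard from day 180 (a 180-day gap can hardly be complete earlier), exits uniform to day 336. P(event) = ∫ λ e^(−λ(u−180)) (1 − p·u/336) du over days 180 to 336, with λ = −ln(S)/156.
- No events from exits: d = 67.5 × (1 − p).

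| Assumed exits p | Spread exits: events, power | No events from exits: events, power |
|---|---|---|
| 0% | 67.5, 86.7% | 67.5, 86.7% |
| 5% | 64.9, 85.4% | 64.1, 85.0% |
| 10% | 62.4, 84.0% | 60.75, 83.0% |
| 15% | 59.8, 82.5% | 57.4, 80.9% |
| 20% | 57.3, 80.8% | 54.0, 78.5% |

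Power of 80% needs 56.1 events, reached at about 22% or 17% exits. The 65/80 row, which starts at 82%, falls to 79.2% or 78.1% at 10%. If abstraction continues after every exit, nothing is lost.

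**Follow-up beyond 48 weeks.** The Schema keeps everyone under observation until the last enrolled patient reaches 48 weeks, and 9.6.4 lists year-2 outcomes. With exits continuing at the same exponential rate:
- p = 10%: 15 extra days give 67.3 events and 86.6%; 30 days give 72.1 events and 88.8%.
- p = 20%: 30 extra days give 65.7 events and 85.8%; 35 days give 67.0 events and 86.5%.

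Under even accrual the average extra follow-up is half the accrual period. So 15 days corresponds to enrolling 300 patients in 30 days (10 a day), and 35 days to 70 days (about 4 a day). The documents give no accrual period, but three clinics are unlikely to enrol that fast.

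**Bias, by simulation.** 10,000 log-rank trials per scenario, 150 per arm, hazard from day 180. A share of would-be LTFU patients is instead censored at random on days 0 to 180.

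| True rates | Share censored | Result |
|---|---|---|
| 70/70 | none | 2.4% false positives favouring ALERT |
| 70/70 | 10% or 20%, ALERT only | 6.0% or 13.5% favouring ALERT |
| 70/70 | 10% or 20%, both arms | 4.5% or 4.8% two-sided error |
| 70/70 | 10% ALERT, 5% SOC | about 5.2% two-sided error |
| 70/85 | none | 87.8% power |
| 70/85 | 10% or 20%, SOC only | 77.7% or 61.6% power |
| 70/85 | 10% or 20%, both arms | about 85% or 82% power |

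Independent repeats agreed to within about 1.5 points.

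**The case for a change.** The strongest case for acting is the bias. Section 8.1 concerns discontinuation, and the one criterion the protocol spells out is carried out as removal plus censoring, so abstraction might be read as stopping for the others too. The arms differ in contact: five modules and continuous outreach against a yearly study visit, so occasions to ask to leave also differ. At a 20% share, about nine patients of 150 (20% of the 45 would-be events) censored in ALERT alone raise false positives favouring it more than fivefold. A sentence on post-exit abstraction would add no patients.

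Part of this stands. The composite wording is wrong, incarceration censoring does remove events, and continuation after 8.1.1 to 8.1.5 is not explicit. The large figures, however, need every informative exit to fall in one arm, every one to be a would-be event, and all to be censored before day 180. Nothing in the documents points to that pattern. Several exits (pregnancy, a life-threatening condition, an IRB decision) have no stated link to disengagement.

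The text also leans towards continuation: quarterly abstraction for every subject, all randomized patients analysed, censoring tied to the last extraction, and no removal for a missed annual visit. Abstraction after a patient withdraws also depends on consent wording that is not in the supplied text.

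**Conclusion.** No change to the plan follows. The composite label is a clerical slip: the outcome is stated as LTFU alone wherever it is defined, and Table 5 can only be read as LTFU-free rates. The decision it is meant to justify is right for the main form of attrition, because loss from clinic care is the event.

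No shortfall from 87% is shown. At an assumed 10% of non-LTFU exits, power is about 83 to 84% with follow-up ending at 48 weeks, and 86.6% with about 15 more days on average. Less favourable Table 5 rows have less room, but the same extra follow-up helps them. Incarceration censoring is deliberate and stated; its frequency is not given, and the planning rates may already be net of it.

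The unwritten rule on abstraction after 8.1.1 to 8.1.5 exits is a detail that analysts would sensibly fill under the intention-to-treat principle, and the SAP, whose detail is not in the supplied text, may already settle it. This conclusion rests on three assumptions: exits well below about 17 to 20%, no strong imbalance of informative exits between arms, and some follow-up beyond 48 weeks. It would need another look if abstraction did stop at exit and such exits proved clearly uneven between arms.

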9.5 Monitoring

Monitoring will be conducted monthly by the core protocol team to assess for accrual and data completeness.

9.6 Analyses

9.6.1 Statistical Analysis Plan

In general, analyses will incorporate the intent-to-treat principle, namely, all randomized participants will be included in the analysis. The primary analysis compares the ALERT Intervention to the SOC arm. For all secondary analyses of interest, no adjustments for multiple comparisons will be made, and a p-value of 0.05 will be considered statistically significant. Demographic and baseline measurement variables will be summarized via standard descriptive statistics.

9.6.2 Analysis of Primary Outcome

A survival analysis of "time to LTFU" will be conducted. LTFU is defined as no visit with a prescribing HIV provider in the last 180 days. Time-to-LTFU will be calculated as total days between the first visit and the date when the participant reaches the definition of LTFU.

For example, a subject has his first visit on Jan 1, 2013, and another visit on Mar 1, 2013. If the subject does not have any visits thereafter, or does not have any visits until >180 days later, the subject will be counted as reaching the primary endpoint of LTFU. In this case, the subject would be LTFU if no visit occurred before Aug 27, 2013, (which is 180 days past Mar 1st). The "time-to-LTFU" will be the time period between Jan 1, 2013 and Aug 27, 2013.

At the end of the study, patients who have not reached the primary endpoint will be censored at the time of their last quarterly data extraction.

Patients who meet the primary endpoint and are found to be incarcerated will be removed from the study and censored effective at the time of their incarceration. Those who are incarcerated but return to care upon release, prior to reaching a primary endpoint, will be allowed to remain in study. Patients who change care provider to an external health facility (such as a different clinic system or a nursing facility) will be assessed for their current engagement in care; those who have completed a clinic visit with a prescribing clinician within the 180 days will be considered engaged in

care, and will not be considered LTFU. If possible, these patients will continue to come in for annual study visits.

The null hypothesis is that the median time-to-LTFU estimated using the Kaplan-Meier method will be identical in both groups. The log-rank test will be used to test the null hypothesis against the alternate hypothesis that the median time-to-LTFU is not the same between the groups.

In addition, to assess the factors associated with time-to-LTFU, Cox regression models will be performed on two subgroups, looking at each arm separately. The model will have time to LTFU as the outcome, baseline variables such as demographic, socioeconomic, psychosocial factors, risk behavior, substance use and psychiatric illness as predictors.

Randomization will be stratified by clinic site and whether the subject is newly diagnosed or returning to care. A total of 300 subjects (150 per arm) will be randomized and followed for a minimum of 48 weeks. SOC will be the clinic standard.

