trial to evaluate the effectiveness of a clinic-based HIV Active Linkage, Engagement, and Retention to Treatment (ALERT) specialist on improving endpoints of retention in care and maintenance of antiretroviral therapy (ART) as compared to the current standard of care (SOC) in HIV primary

care clinics.

Duration: Each subject will receive follow-up of at least 48 weeks. Follow-up for

enrolled patients will continue until the last enrolled patients has been

on study for 48 weeks

Sample Size: A total of 300 subjects will be randomized, 150 per arm.

Study Population: Eligible subjects will include 1) newly diagnosed HIV-infected individuals

entering primary HIV care at one of the CCTG clinics, or 2) previously diagnosed HIV-infected individuals who are "out of care" defined as having no visit with a prescribing HIV provider in the last 180 days and

not on a stable ARV regimen.

Stratification: Subjects will be stratified based on study site and if they are newly

diagnosed or returning to care. (See Diagram 1)

Intervention: Subjects will be randomized (1:1) to either the ALERT Enhanced Retention

Intervention Arm or the SOC Arm. Subjects placed into the ALERT Intervention Arm will receive aggressive engagement efforts by the ALERT specialist to ensure visit continuity and retention into care. The ALERT specialist will also administer an education intervention consisting of 5 retention modules designed to improve HIV knowledge and self-efficacy, and will also monitor health care visits and intervene via

methods to track, find, and re-engage patients during the study. Patients placed into the SOC arm will receive the HIV care clinic's current standard

[figure not shown]
of care retention services.

Outcomes:

Primary Outcome: Time to "lost to follow up" (LTFU) defined as the time from study entry to

no visit with a prescribing HIV provider in the last 180 days

DIAGRAM 1: CCTG 594 STUDY SCHEMA

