4.2 Exclusion Criteria

- 4.2.1 Unstable neurologic, psychiatric, or physical condition which, in the opinion of the investigator, would limit participation with study procedures for the duration of the study.
- 4.2.2 A level of drug or alcohol use that, in the opinion of the investigator, would preclude safe participation in the study.
- 4.2.3 Resident of nursing home or skilled facility.
- 4.2.4 Pregnant or breastfeeding
- 4.2.5 Patient's first primary care visit (for new patients) or return to care visit

(for patients returning to care) occurred >60 days ago

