6.2.2 Entry Evaluations and Randomization

Entry must occur within 60 days of the patient's first primary care visit (for patients new to care) or their first primary care re-entry visit (for patients returning to care). At study entry, baseline surveys will be collected utilizing the web-based, computer-assisted system on the study specific portal (to view baseline survey, see Attachment 5, *iPad Assessments for CCTG 594*). The portal will allow private completion of questionnaires without concern that clinic or study personnel can view the subject's responses in order to encourage candor.

Subjects will be randomized (1:1) to SOC or ALERT Intervention study arm. Randomization will be stratified by clinic site and whether the subject is newly diagnosed or returning to care. A total of 300 subjects

(150 per arm) will be randomized and followed for a minimum of 48 weeks. SOC will be the clinic standard.

Samples of plasma will be stored for future assays.

6.2.3 On-Study Evaluations

Study specific follow-up visits for each subject will be kept to a minimum in order not to bias the outcome of lost to follow up. Our experience suggests that involvement in a research protocol, with the extra effort the coordinators exert to ensure study follow-up, could easily impact on attendance to clinical care. Thus, for SOC patients, study specific visits will occur yearly preferably in conjunction with a regularly scheduled clinic visits (see below, *yearly study visits*).

In the ALERT intervention arm, the ALERT specialist will conduct 5 monthly educational retention modules (in person or by phone). The ALERT specialist will also continuously monitor and track all health care visits to ensure healthcare continuity, and will intervene using described tools/methods when the subject does not have a visit within a predetermined interval (see Attachment 4, *Manual of Operating Procedures*, for ALERT Specialist job description, methods, and Retention Modules).

6.2.4 Data Abstraction

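### The primary time-to-LTFU clock has two possible origins, because the first visit in section 9.6.2 is undefined and may precede randomisation by up to 60 days; the worked example is also one day off its own 180-day rule

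*Combined protocol and SAP*

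**What the plan says.** The start of the primary clock is worded differently in three places.

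- Schema, Primary Outcome: "defined as the time from study entry to" the point at which the 180-day criterion is met.
- Section 9.2: "defined as the time from baseline visit to meeting the primary endpoint".
- Section 9.6.2, the calculation rule: "Time-to-LTFU will be calculated as total days between the first visit and the date when the participant reaches the definition of LTFU".

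Section 6.2.2 has the baseline surveys collected at study entry, with randomisation following, and Table 1 puts the assessments and randomisation in the same column. The Schema and section 9.2 therefore name one time point.

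The first visit in 9.6.2 is not defined. Its worked example begins: "a subject has his first visit on Jan 1, 2013, and another visit on Mar 1, 2013". The clock starts on 1 January, and the visits described are those that drive the 180-day gap.

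On timing, section 6.2.2 says "Entry must occur within 60 days" of the first primary care visit or the re-entry visit. Section 4.2 sets the same limit as an exclusion, for a first or return visit that "for patients returning to care) occurred >60 days ago".

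The example then fixes the event date: the participant is lost "if no visit occurred before Aug 27, 2013, (which is 180 days past Mar 1st"). Section 9.2 requires more than 180 days without a visit.

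**The concern.** Participants are comparable by design from randomisation. If the first visit is the first care visit, each participant's time includes a stretch before any arm existed, during which LTFU cannot occur. Two programmers working from the Schema and from 9.6.2 could produce different event times, curves and medians from the same data.

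Section 9.4.1 plans on endpoint-free percentages (70% against 85%) without naming an origin, so observed retention cannot be set against the planning assumption until one is chosen.

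The example should settle how the event date is computed. As written, a patient whose next visit is on 27 August has no visit before that date and counts as lost, although only 179 days have passed.

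**Working it through.** **1. The plan's own figure.** Inputs from section 9.4.1 and Table 5: 150 per arm, two-sided alpha 0.05, 70% and 85% endpoint-free.

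- HR = ln(0.70)/ln(0.85) = 2.195 (plan: 2.19).
- Expected events = 150 × (0.30 + 0.15) = 67.5.
- Freedman log-rank power = Φ(√67.5 × (2.195 − 1)/(2.195 + 1) − 1.96) = Φ(8.216 × 0.374 − 1.96) = Φ(1.11) = 86.7% (plan: 87%).

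The figure reproduces, so 70% and 85% serve as anchors below.

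**2. The example patient.** From 1 January to 27 August 2013 is 238 days. If entry was 60 days after the first visit, time from entry is 238 − 60 = 178 days. A common lag of d days moves the whole curve, and any median that is reached, by d days.

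**3. When events can occur.** On the care-visit reading the earliest LTFU is about day 180 from the first visit. Entry is by day 60. No LTFU event can therefore precede randomisation, and the earliest falls 180 − 60 = 120 days after it.

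**4. Shift in retention at day 336 (48 weeks).** The documents give neither the hazard shape nor the lag distribution, so two assumptions are shown. Each cell is SOC vs ALERT.

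*A. 70%/85% hold at day 336 from the first visit; no events before day 180; constant hazard afterwards.* Retention at day 336 counted from randomisation is S^((156 + d)/156), where 156 = 336 − 180.

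*B. 70%/85% hold at day 336 from randomisation; constant hazard from day 0.* Retention at day 336 counted from the first visit is S^((336 − d)/336).

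| Lag d (days) | A: from randomisation | Difference | B: from first visit | Difference |
|---|---|---|---|---|
| 0 | 70.0% vs 85.0% | 15.0 | 70.0% vs 85.0% | 15.0 |
| 30 | 65.4% vs 82.4% | 17.0 | 72.3% vs 86.2% | 14.0 |
| 60 | 61.0% vs 79.8% | 18.8 | 74.6% vs 87.5% | 12.9 |
| Uniform 0–60 (mean) | 65.4% vs 82.4% | 17.0 | 72.3% vs 86.2% | 14.0 |

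Under A the shift runs from 0 to 9.0 points in SOC and 0 to 5.2 in ALERT; with uniform lags it is 4.6 and 2.6. Under B it runs from 0 to 4.6 and 0 to 2.5; with uniform lags, about 2.3 and 1.2. In both, counting from the first visit gives higher retention and a smaller difference between arms.

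**5. Effect on the log-rank test.** Simulation of 1,500 trials per scenario, hazards as in B, lag uniform on 0–60 days in both arms:

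| Follow-up | Quantity | From entry | From first visit |
|---|---|---|---|
| Fixed 336 days | Type I error | 4.7% | 4.7% |
| Fixed 336 days | Power | 89.6% | 89.7% |
| 336–700 days (assumed) | Type I error | 4.4% | 4.5% |
| 336–700 days (assumed) | Power | 96.1% | 95.9% |

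The 89.6% exceeds the 86.7% in step 1 because Freedman's formula is the more conservative; Schoenfeld's gives 89.8%. In two further simulations with an assumed 12-month accrual (4,000 and 3,000 trials per effect size), the two origins gave different test decisions in 0.1–1.8% and 0.07–1.6% of trials.

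**6. The example date.** 1 March 2013 + 180 days = 28 August; 27 August is day 179. If the rule is more than 180 days, it is first met on day 181, 29 August. Time from 1 January is then 240 days, against 238 in the example.

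**The case against.** *The term may simply mean the baseline visit.* Where the protocol means a care visit it usually says so, as in sections 4.2, 6.2.1 and 6.2.2. If the first visit is the baseline visit, all three places agree. This stands in part: the care-visit reading is likely but not stated, and what is shown is an undefined term. However, no passage equates the two. The first study visit would be screening, which Table 1 allows up to 30 days before entry.

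*The primary inference does not move.* This stands. The lag precedes randomisation, so it is balanced between arms on average, and no LTFU event can fall before randomisation. A reader might infer immortal-time bias or lost power; the timing rules and the simulations do not support that.

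*The plan does not call for retention at day 336.* This also stands. Section 9.6.2 plans a log-rank test and Kaplan-Meier medians, and section 9.4.1 ties 70% and 85% to no time point. The shifts in points illustrate how far the curve moves. Nine points needs assumption A and every participant entering on day 60.

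*A separate SAP may settle it.* Section 9.0 says a SAP provides details and takes precedence. No text beyond section 9 was available, so this cannot be excluded. The protocol sections would still need to agree.

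*The date slip is one day and the same in both arms.* True. It concerns the event date, not time zero, and can reclassify only borderline gaps.

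**Conclusion.** The point holds as an inconsistency in definition. There are two candidate origins: study entry, which is also the baseline visit, and an undefined first visit that is probably a care visit up to 60 days before randomisation. A reader who counts three wordings might infer three origins, but section 6.2.2 makes the first two one.

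On the care-visit reading the reported curve and medians change. The size at day 336 is about 0 to 9 points, or roughly 3 to 5 points with uniform lags under assumption A and about 1 to 2 under assumption B. These figures rest on assumed hazards and lags. The log-rank comparison is essentially unaffected.

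The one-day error in the example is certain and separate. It contradicts both the 180-day definition and the stricter wording in section 9.2.

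The same undefined origin is used for time to ART initiation in section 9.6.3. There the reassurance about early events does not carry over: the eligibility criteria do not bar a newly diagnosed patient from starting ART between the first care visit and entry, so a start before randomisation could be counted as an event.

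**What to change.** 1. Name the randomisation date as time zero in the Schema and in sections 9.2, 9.6.2 and 9.6.3.
2. Give one formula for the LTFU event date that matches the definition, for example last prescriber visit plus 181 days if more than 180 days is intended. Use the same threshold wording throughout.
3. State whether the 180-day gap may run from a care visit before randomisation. If it may, an event can occur as early as about 120 days after randomisation; changing the origin alone does not settle this.
4. Recompute the example's event date and elapsed time, and show the randomisation date in it.
5. If a separate SAP exists, confirm that it says the same.

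The cost is wording only. Care-visit dates are already abstracted for the endpoint and randomisation dates should be held in the data system, so no new data collection or change in sample size is needed.
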